surgical trauma and postoperative pain, low bleeding complication rates, shorter hospital length of stay and increased patient satisfaction.^{1 2} Robotic-assisted surgery (RAS) has emerged as an alternative minimally invasive surgical option, providing increased ergonomics, magnification of the surgical field, greater amplitude of movement and higher precision.³

Despite the growing applicability of RAS, the need of pneumoperitoneum and steep head-down (Trendelenburg) position could have a marked influence on patients respiratory mechanics. Indeed, this could lead to increased intra-abdominal pressure and cephalic elevation of the diaphragm, decreasing the compliance of the respiratory system and tidal volume, as well as increasing the plateau and peak pressure.⁴⁻⁸

Postoperative pulmonary complication (PPC) usually occur between 5 and 7 days after surgery and include the development of respiratory events, such as acute respiratory failure, acute respiratory distress syndrome (ARDS), pneumonia, prolonged or unplanned mechanical ventilation, reintubation, hypoxemia, atelectasis, bronchospasm, pleural effusion, pneumothorax and respiratory depression.⁹ Approximately, 5% of patients submitted to surgery develop at least one PPC during the follow-up, resulting in longer hospital length of stay and higher mortality rates.¹⁰ The changes in respiratory mechanics induced by the surgical positioning and by the degree of pneumoperitoneum during RAS could increase the risk of PPC in this group of patients. Nevertheless, there are currently insufficient data to guide the best ventilatory strategy during RAS, with some reports suggesting that ventilatory parameters should be adjusted to maintain normocapnia, despite the associated need for high tidal volumes.^{8 11}

The aim of the AVATaR study is to investigate the incidence of PPC, characterise current ventilatory practices and evaluate the association between ventilatory parameters and outcomes in surgical patients undergoing general anaesthesia for RAS.

METHODS

Design

This is an international multicenter prospective observational study designed in accordance with the declaration of Helsinki, registered at www.clinicaltrials.gov (trial identification number NCT02989415).

Patient and public involvement

Patients or public were not involved in the study design.

Patient eligibility

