| Obstructive sleep apnoea | n/Total (%) |
| Active neoplasia | n/Total (%) |
| Liver cirrhosis | n/Total (%) |
| Anaemia ($\text{Hb} < 10\text{ g/dL}$) | n/Total (%) |
| Chronic kidney disease | n/Total (%) |
| Haematological disease | n/Total (%) |
| Use of immunosuppression | n/Total (%) |
| Complications ≤ 30 days before surgery | |
| None | n/Total (%) |
| Respiratory infection | n/Total (%) |
| Use of mechanical ventilation | n/Total (%) |
| Transfusion of blood products | n/Total (%) |
| Vital signs | |
| Respiratory rate, mpm | Mean \pm SD |
| Heart rate, bpm | Mean \pm SD |
| Mean arterial pressure, mm Hg | Mean \pm SD |
| SpO_2 , % | Mean \pm SD |
| Laboratory tests | |
| Haemoglobin, g/dL | Mean \pm SD |

Continued

Table 1 Continued

| All patients (n=) | |
|------------------------------|---------------|
| Leucocytes, $\times 10^9/L$ | Mean \pm SD |
| Creatinine, mg/dL | Mean \pm SD |
| Condition of the procedure | |
| Elective | n/Total (%) |
| Urgency | n/Total (%) |
| Emergency | n/Total (%) |
| Expected duration of surgery | |
| ≤ 2 hours | n/Total (%) |
| 2–3 hours | n/Total (%) |
| >3 hours | n/Total (%) |
| Incision | |
| Peripheral | n/Total (%) |
| Low abdomen | n/Total (%) |
| High abdomen | n/Total (%) |
| Intrathoracic | n/Total (%) |
| Other | n/Total (%) |
| Surgical procedure | |
| Prostatectomy | n/Total (%) |
| Nephrectomy | n/Total (%) |
| Hysterectomy | n/Total (%) |
| Bariatric | n/Total (%) |
| Sacrocolpopexy | n/Total (%) |
| Cholecystectomy | n/Total (%) |
| Cardiac | n/Total (%) |
| Colorectal | n/Total (%) |
| Hernia | n/Total (%) |
| Head and neck | n/Total (%) |
| Pulmonary resection | n/Total (%) |
| Cystectomy | n/Total (%) |
| Pyloroplasty | n/Total (%) |
| Pyeloplasty | n/Total (%) |
| Other | n/Total (%) |

ARISCAT, assess respiratory risk in surgical patients in Catalonia; ASA, American Society of Anesthesiology; BMI, body mass index; bpm, beats per minute; COPD, chronic obstructive pulmonary disease; Hb, haemoglobin; mpm, movements per minute; SpO₂, pulse oximetry.

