| Red blood cells | n/Total (%) |
| Fresh frozen plasma | n/Total (%) |
| Platelets | n/Total (%) |
| Cryoprecipitate | n/Total (%) |
| Duration of surgery, min | Mean±SD |
| Duration of anaesthesia, min | Mean±SD |

controlled environment to maintain confidentiality. Electronic documents are controlled with password protection according to best practices.

Data management

The goal of the clinical data management plan is to provide high-quality data by adopting standardised procedures to minimise the number of errors and missing data, and consequently, to generate an accurate database for analysis. Remote monitoring is performed to signal early aberrant patterns, issues with consistency, credibility and other anomalies, according to predefined queries created in the system. Any missing and outlier data values are individually revised and completed or corrected whenever possible.

Cleaning and locking of the database

The database will be locked as soon as all data are entered and all discrepant or missing data are resolved—or if all efforts are employed and we consider that the remaining issues cannot be fixed. At this step, the data will be reviewed before database locking. After that, the study database will be locked and exported for statistical analysis. At this stage, permission for access to the database will be removed for all investigators and the database will be archived.

Sample size

All patients submitted to ventilation during general anaesthesia for RAS will be consecutively included during the period of 1 month, in a convenience sample.

Predefined statistical analysis plan

For the primary analyses, only patients undergoing abdominal surgery will be included. Also, patients in whom the surgery was converted to open or laparoscopic will be excluded. This group of patients excluded due to these reasons will be studied in a separate report. Continuous distribution of the data will be assessed by visual inspection of histograms and D'Agostino-Pearson's normality tests. Baseline characteristics will be expressed as counts and percentages, means and SD or medians and IQR whenever appropriate. Hypothesis tests will be two-sided with a significance level of 5%. We will not adjust p values for multiple comparisons. Analyses will

be performed using the R (R Core Team, 2016, Vienna, Austria) programme.

Baseline characteristics

Patients baseline characteristics will be presented as shown in mock [table 1](#).

Intraoperative characteristics

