Intraoperative characteristics will be presented as shown in mock [table 2](#).

Ventilatory variables

Ventilatory variables and other interventions will be reported hourly for 6 hours and in four specific periods: (1) 5 min after induction and beginning of ventilation (T_1); (2) 5 min after CO_2 insufflation (T_2); (3) 5 min after definitive positioning (immediately before beginning surgery) (T_3) and (4) 5 min after removal of pneumoperitoneum and return to supine (T_4). Peak, plateau and driving pressure (defined as plateau minus positive-end expiratory pressure (PEEP)) and PEEP levels, tidal volume size, respiratory rate, fraction of inspired oxygen (FiO_2), static and dynamic respiratory system compliance, pulse oximetry (SpO_2), heart rate, mean arterial pressure and pressure of CO_2 insufflation over the four specific periods will be analysed using a mixed model with repeated measures and plotted in an interaction plot (mock [table 3](#)).

Primary outcome

The number of patients developing a PPC will be reported in absolute numbers and percentages (mock [table 4](#)). The impact of ventilatory variables on the development of PPC will be assessed using a generalised linear mixed-effect model. Relevant covariates included in the final multivariable model will be identified as those with $p<0.2$ in the univariable model (including centre as a random effect), clinical relevance and no statistical association with other relevant variables. In the final model, time of measurement will be included as a fixed effect together with the variables of interest and the centres and patients will be included as random effect. The linearity of each continuous predictor with the log odds outcome will be checked graphically and, if not present, a log-transformation will be performed. Pearson correlation coefficients will be used to assess collinearity between predictors. Since a high collinearity between peak, plateau and driving pressure is expected, the main model will consider the variable with the higher amount of measurements between peak or plateau pressure. Driving pressure will be considered in a sensitivity analysis, excluding PEEP, peak and plateau pressure. Finally, the intraclass correlation coefficient (ICC) will be assessed. The ICC represents the ratio of between-site variance to total variance, ranging from 0 to 1.

Secondary outcomes

Secondary outcomes will be reported as shown in mock [table 4](#).

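### The covariate rule for the ventilation–PPC model (univariable p<0.2, clinical relevance, no association with other variables) can discard true confounders; a short named set should be forced in instead

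*SAP*

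**What the plan says.** The Primary outcome section of the SAP has two parts. The first reports the number and percentage of patients with a PPC. The second is a model: "The impact of ventilatory variables on the development of PPC will be assessed using a generalised linear mixed-effect model". Its covariates are set by this rule: "Relevant covariates included in the final multivariable model will be identified as those with $p<0.2$ in the univariable model (including centre as a random effect"). In full, the criteria are "those with $p<0.2$ in the univariable model (including centre as a random effect), clinical relevance and no statistical association with other relevant variables". The final model also carries time of measurement as a fixed effect, and "the centres and patients will be included as random effect". Collinearity between predictors is checked separately by Pearson correlation.

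The SAP names no confounder that must be in the model and gives no list of candidates. It does not say how the three criteria combine or how clinical relevance is judged.

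On size, the Sample size section describes a one-month convenience sample without a number. The primary analyses are limited to abdominal surgery without conversion. The only PPC rate is in the Introduction and refers to surgery in general: "5% of patients submitted to surgery develop at least one PPC".

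**The concern.** The model is meant to estimate the effect of ventilatory variables, so its covariates are there to remove confounding. A confounder is defined by its relation to both the ventilator setting and the outcome. The rule works against this in two ways.

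- **The p-value step** looks only at the crude relation with PPC, in the same data. With few events a real confounder often fails by chance. If it raises PPC risk but goes with lower values of a harmful setting, the two effects offset each other and its crude association looks weak however important it is.
- **The no-association step** removes variables related to other relevant variables. If those include the ventilatory variables, the step removes covariates because they have one of the two properties of a confounder. If it means other covariates only, it duplicates the planned collinearity check and leaves the choice within a correlated pair open.

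Clinical relevance, as a further joint condition, can remove noise variables but cannot bring back a confounder that failed either statistical step. At stake is whether the reported odds ratios for ventilatory variables are adjusted for the right things.

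**Working it through.** The SAP has no planning figure to reproduce. The checks below cover the p-value step only, with one row per patient and no centre effect. All sample sizes, PPC rates, prevalences and effect sizes are assumed, apart from the 5% rate taken from the Introduction.

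**1. Null variables.** Each passes p<0.2 with probability 0.20 by definition. Among 20 independent null candidates, 0.2 × 20 = 4 are expected to pass, and P(at least one) = 1 − 0.8^20 = 0.99. This is before clinical relevance is applied.

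**2. Binary confounder missed by chance.** Let p0 and p1 be the PPC risks without and with the factor, and d = p1 − p0. SE0 is the pooled standard error and SE1 the unpooled one. The two-sided 0.2 level has z = 1.2816, and

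P(missed) ≈ Φ[(1.2816 × SE0 − d) / SE1].

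Example: 1000 patients, 5% PPC (50 events), prevalence 30%, odds ratio 1.5.
- 0.7·p0 + 0.3·p1 = 0.05 gives p0 = 0.0438, p1 = 0.0644, d = 0.0205.
- SE0 = √[0.05 × 0.95 × (1/700 + 1/300)] = 0.0150; SE1 = √[0.0438 × 0.9562/700 + 0.0644 × 0.9356/300] = 0.0161.
- (0.0193 − 0.0205)/0.0161 ≈ −0.08, so P(missed) = 0.47.

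Ranges over prevalences of 10% and 30%:

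| Events (basis) | OR 1.3 | OR 1.5 | OR 2.0 |
|---|---|---|---|
| 25 (5% of 500) | 74–78% | 62–70% | 35–50% |
| 50 (5% of 1000) | 65–73% | 47–61% | 16–34% |
| 100 (5% of 2000) | 52–66% | 27–47% | 3–15% |
| 200 (10% of 2000 or 20% of 1000) | 35–58% | 10–36% | 0–6% |

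**3. Direction of confounding.** Logistic simulation, 500 runs per size: exposure log odds ratio 0.4 per SD, and two binary confounders with conditional odds ratio 1.5, one positively and one negatively correlated with the exposure.

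| Mean events | Positive one missed | Negative one missed |
|---|---|---|
| 29 | 42% | 82% |
| 57 | 22% | 78% |
| 111 | 8% | 79% |
| 222 | 1% | 79% |

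The last column does not improve with size because masking here is almost complete. Patients with the negatively correlated factor have a mean exposure 0.79 SD lower, so its crude log odds ratio is about ln 1.5 − 0.79 × 0.4 = 0.405 − 0.316 = 0.09. The other confounder lowers it further, to a crude odds ratio of about 1.04. The screen treats it as a null variable and misses it about 80% of the time. This is a deliberately extreme case.

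**4. Effect on the exposure estimate.** One continuous confounder, odds ratio 1.5 per SD, correlation −0.5 with the exposure, true exposure log odds ratio 0.30, 5% PPC. Its crude log odds ratio is about 0.405 − 0.5 × 0.30 = 0.255, so masking is partial. Always omitting it would bias the exposure log odds ratio by about 0.405 × (−0.5) = −0.20. Two independent sets of runs under the screen gave:

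| Events | Missed | Bias |
|---|---|---|
| about 25 | 51% | −0.06 to −0.08 |
| about 50 | 33–34% | −0.04 to −0.05 |

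Against 0.30 this is a relative bias of 20–27% and 13–17%. One set was carried to 100 and 200 events: missed 10% and 2%, bias −0.01 and 0.00. With the confounder forced in, bias was within ±0.01 at every size.

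**The case against.** The strongest case for the plan is that this is an exploratory association model, that clinical judgement is part of the rule, and that the harm is often small. The last point has force. A simulation with three confounders of odds ratio 1.3 per SD, correlated 0.2 to 0.3 with the exposure in the same direction as its effect, plus ten noise candidates, gave a screened bias of at most 0.035 against a standard deviation of 0.09 to 0.24. Coverage was 92.5–96.5%, against 92.8–96.5% for a forced-in set. The damage is therefore confined mainly to masked confounding and small event counts.

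Four stronger readings are tempting and are not supported.

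- **That the expected number of events is known to be low.** The SAP gives none. The 5% is a background rate for surgery in general, and this composite counts unplanned oxygen.
- **That every row of Tables 1 and 2 is a candidate, so many noise variables enter.** Those tables are introduced for presentation only. Clinical relevance stands between a small p-value and the model, so 20% is the pass rate of one step, not of the rule.
- **That the screen double-counts patients.** The SAP does not say that it runs on repeated readings. With one row per patient, a centre effect alone suits a baseline covariate, so the missing patient effect is not itself an error.
- **That the odds ratios will generally be biased.** The check just given shows otherwise for same-direction confounding.

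Clinical relevance might also be meant as an alternative way in. The wording joins the criteria with 'and', so the joint reading is the natural one, but the text should settle it.

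**Conclusion.** The point stands in a limited form. The rule is stated, not merely left open, and on its natural reading two of its three criteria can remove true confounders from a model whose purpose is to estimate the effect of ventilatory variables. The loss is material at about 25 to 50 events: moderate confounders are missed about half the time or more, and a partly masked confounder shifts the exposure log odds ratio by 13–27% of its value. At about 100 to 200 events or more the bias is small in most settings. Weak binary confounders are still often missed there, but each carries little confounding. A strongly masked one can be missed at any size.

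These sizes rest on assumed patient numbers, PPC rates, effects and correlations, and on the p-value step alone; the no-association step was not simulated. The descriptive PPC incidence, which is the primary outcome itself, is untouched. The change should be made, but the study's main result does not depend on it.

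**What to change.** In the Primary outcome section, delete the p<0.2 and no-association criteria for confounders. Name instead a short set, fixed before ventilation starts and drawn from Table 1: for example the ARISCAT score (expanded in the table's footnote as "assess respiratory risk in surgical patients in Catalonia"), BMI and procedure group, with ASA class or COPD added if events allow. Keep the set in the model whatever its p-values.

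State how model size will be limited to the observed events. With 10 model parameters in total, 25, 50 and 100 events give 2.5, 5 and 10 events per parameter, so a long list would recreate the problem. State also that variables that may be consequences of ventilation, such as intraoperative fluid balance or blood loss, are not used as confounders. The planned collinearity check among the pressure variables can stay.

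The cost is a wording change, since the named variables are already in Table 1. The downside is that some may prove unimportant and use a few degrees of freedom.

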© Author(s) (or their employer(s)) 2018. Re-use permitted under CC BY-NC. No commercial re-use. See rights and permissions. Published by BMJ.

For numbered affiliations see end of article.

Correspondence to

[name] [name];
[contact]

ABSTRACT

Introduction Robotic-assisted surgery (RAS) has emerged as an alternative minimally invasive surgical option.

Despite its growing applicability, the frequent need for pneumoperitoneum and Trendelenburg position could significantly affect respiratory mechanics during RAS. AVATaR is an international multicenter observational study aiming to assess the incidence of postoperative pulmonary complications (PPC), to characterise current practices of mechanical ventilation (MV) and to evaluate a possible association between ventilatory parameters and PPC in patients undergoing RAS.

Methods and analysis AVATaR is an observational study of surgical patients undergoing MV for general anaesthesia for RAS. The primary outcome is the incidence

of PPC during the first five postoperative days. Secondary outcomes include practice of MV, effect of surgical positioning on MV, effect of MV on clinical outcome and intraoperative complications.

Ethics and dissemination This study was approved by the Institutional Review Board of the Hospital Israelita Albert Einstein. The study results will be published in peer-reviewed journals and disseminated at international conferences.

Trial registration number NCT02989415; Pre-results.

INTRODUCTION

Minimally invasive surgery is increasingly being used due to its association with reduced

Strengths and limitations of this study

- ▶ This will be the first study to assess the incidence of postoperative pulmonary complications and the ventilatory practice in patients undergoing general anaesthesia for robotic surgery.
- ▶ This is a multinational, multicenter, prospective, observational, rather than retrospective, study and should enhance our understanding of the incidence of postoperative pulmonary complications and the ventilatory practice in this group of patients.
- ▶ Ventilatory variables will be measured at the critical points of the surgery, to assess the impact of surgical positioning and of the pneumoperitoneum in respiratory mechanics.
- ▶ Due to the absence of standardisation on the definition of postoperative pulmonary complications, some complications will not be addressed.

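### The covariate rule for the ventilation–PPC model excludes on any statistical association, not only strong collinearity, and so can discard confounders; no cut-off, comparison set or retention rule is given for covariates

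*SAP*

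**What the plan says.** Estimating how ventilation relates to outcome is a stated aim. The Abstract sets out "to evaluate a possible association between ventilatory parameters and PPC in patients undergoing RAS", and the Introduction closes with the intention to "evaluate the association between ventilatory parameters and outcomes in surgical patients undergoing general anaesthesia for RAS".

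The model for this is in the Predefined statistical analysis plan, under Primary outcome. It is a generalised linear mixed-effect model for PPC. A covariate has to meet three conditions: p<0.2 in a univariable model with centre as random effect, and then "clinical relevance and no statistical association with other relevant variables". The covariates that pass join a model already fixed in its other terms: "time of measurement will be included as a fixed effect together with the variables of interest", plus random effects for centre and patient.

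Later in the same paragraph, "Pearson correlation coefficients will be used to assess collinearity between predictors". An action follows for one set only. Either peak or plateau pressure enters the main model, whichever has more measurements. Driving pressure goes into a sensitivity analysis without PEEP, peak or plateau pressure.

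**The concern.** A confounder is associated with both the exposure and the outcome, and two confounders of the same exposure are often associated with each other. A rule that keeps covariates related to PPC and then removes those related to other relevant variables works against adjustment. The condition can be read in three ways:

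- **Other covariates only** (the more natural reading). One of two correlated confounders is lost, even when the correlation is weak and each carries separate information.
- **Ventilatory variables as well.** Confounders are removed by definition.
- **High collinearity only.** A near-duplicate is dropped and little is lost.

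The text does not choose between them. It sets no cut-off, does not say which variables are compared, and does not say which member of an associated covariate pair is kept. Two analysts could follow the plan faithfully, fit different models, and make the choice after seeing the data.

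What is at stake is the odds ratio for the ventilatory variables. Restriction to abdominal surgery and the centre random effect control part of the confounding; control at patient level depends on this rule.

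**Working it through.** **No plan figure to reproduce.** The SAP describes a convenience sample and states no N, event count or effect size. The inputs below are assumptions, except the background rate, for which the Introduction cites about "5% of patients submitted to surgery develop at least one PPC during the follow-up", and the general two-sided 5% significance level.

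**Step 1: how weak an association would exclude a covariate?** The plan attaches no level to this condition. If its only general level, 5%, were used, the smallest significant correlation is about 1.96/√(N − 2 + 1.96²):

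- N = 200: 1.96/√201.84 = 0.14
- N = 500: 1.96/√501.84 = 0.09
- N = 1000: 1.96/√1001.84 = 0.06

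These are far below any level at which collinearity troubles a model.

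**Step 2: bias by hand.** Take an exposure with no effect and two confounders, each with odds ratio (OR) 1.3–1.5 per SD (ln OR 0.262–0.405). Let a be the correlation of each confounder with the exposure and m the correlation between the confounders. On the log-odds scale, the bias is approximately the omitted coefficient times the slope of the omitted confounder on the exposure.

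- One dropped: slope = (a − a·m)/(1 − a²). At a = m = 0.3 this is 0.21/0.91 = 0.231, giving exp(0.231 × 0.262) = 1.06 to exp(0.231 × 0.405) = 1.10.
- Both dropped: exp(2 × 0.3 × 0.262) = 1.17 to exp(2 × 0.3 × 0.405) = 1.28.
- One dropped at m = 0.6: slope 0.12/0.91 = 0.132, OR 1.04–1.05.
- One dropped at m = 0.9: slope 0.03/0.91 = 0.033, OR about 1.01.
- a = 0.1, m = 0.3: one dropped, slope 0.07/0.99 = 0.071, OR 1.02–1.03; both dropped, exp(0.2 × 0.262) = 1.05 to exp(0.2 × 0.405) = 1.08.

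**Step 3: simulation.** n 500 or 1000, PPC 5% or 10%, 20 centres with random-intercept SD 0.5, true exposure OR 1, logistic model with centre random intercept, 2000 data sets per scenario, Wald test at 5%:

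| Correlations (exposure / mutual) | Confounders kept | Exposure OR per SD | False positives |
|---|---|---|---|
| 0.3 / 0.3 | both | 0.99–1.01 | 4–6% |
| 0.3 / 0.3 | one | 1.06–1.10 | 6–12% |
| 0.3 / 0.3 | none | 1.16–1.28 | 10–57% |
| 0.3 / 0.6 | one | 1.03–1.06 | 4–7% |
| 0.3 / 0.9 | one | 1.01–1.03 | 5–7% |
| 0.1 / 0.3 | one | 1.01–1.04 | 4–6% |
| 0.1 / 0.3 | none | 1.05–1.09 | 5–11% |

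The simulation agrees with the hand calculation. Dropping one of a pair costs most when the two are weakly related and almost nothing when they are near-duplicates, so a rule triggered by any association does its damage where it has least reason to act.

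**Step 4: price of keeping both.** At a = m = 0.3 the covariates explain R² = (0.09 + 0.09 − 2 × 0.09 × 0.3)/(1 − 0.09) = 0.126/0.91 = 0.14 of the exposure's variance, so its standard error grows by 1/√(1 − 0.14) = 1.08. The simulated rise was 6–10% at exposure correlation 0.3 and 2–4% at 0.1.

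**Not simulated:** the patient random effect and repeated rows, the time effect, and several ventilatory variables at once. How often a covariate would be dropped cannot be given, because the rule has no cut-off.

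**The case against.** The best defence is that the authors meant collinearity. The paragraph goes on to Pearson coefficients, expects high collinearity among the airway pressures and handles it. It also has a separate term for the exposures: "time of measurement will be included as a fixed effect together with the variables of interest". The condition belongs to a sentence about covariates, so its relevant variables are most naturally the other covariates.

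Much of this stands, and it rules out some stronger inferences a reader might draw:

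- *That the plan bars every confounder.* This needs the ventilatory variables to be among the relevant variables, which the text neither says nor excludes. The 1.16–1.28 range for both dropped belongs mainly to that reading.
- *That the plan offers no test or tie-break at all.* Pearson correlation is named for predictors, and there is a rule for the airway pressures. But Pearson has no cut-off, is not tied to this condition and does not suit multi-category covariates such as procedure. The pressure rule concerns exposures.
- *That the Introduction shows which confounders would be lost.* It describes pneumoperitoneum and head-down position as "decreasing the compliance of the respiratory system and tidal volume, as well as increasing the plateau and peak pressure", mainly a pathway through the exposure. A cause of airway pressure confounds only if it also reaches PPC by another route, which is not stated. The remark that "ventilatory parameters should be adjusted to maintain normocapnia, despite the associated need for high tidal volumes" concerns how settings are chosen and names no PPC risk factor.

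The defence does not supply the missing limit. The condition speaks of statistical association, and no sentence restricts it to high collinearity.

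**Conclusion.** The point holds as a wording defect with a real risk of bias for a stated aim; it should be fixed. Applied as written to the other covariates, the rule can discard one of two weakly correlated confounders, and under the assumed inputs a null exposure then shows an OR of about 1.06–1.10 per SD. If the ventilatory variables are also compared, both confounders can go and the OR is about 1.16–1.28. The bias is small if confounders correlate only 0.1 with the exposure, and negligible if only near-duplicates are dropped.

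These figures rest on assumed correlations and confounder effects and on a simpler model than the planned one. The direction carries over; the exact ORs and false-positive rates may not. A reader might infer that the primary result is compromised. It is not: PPC incidence is a count and percentage and does not use this model.

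**What to change.** Replace the condition on statistical association with wording such as: *Clinically relevant baseline and surgical covariates will not be excluded because they are associated with the ventilatory variables or with each other. Only near-duplicate covariates, above a prespecified high correlation threshold, will be reduced to one, keeping the clinically more relevant.* State the threshold in the SAP. Leave the rule for peak, plateau and driving pressure as it is.

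Keep the covariate set short and chosen on clinical grounds. At the cited 5% rate, an assumed 500 patients give 500 × 0.05 = 25 events, and the ventilatory variables also use model terms.

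The cost is a change of wording; the candidate covariates are already in mock Tables 1 and 2. Intervals widen modestly, with a standard error about 6–10% larger at exposure correlation 0.3, and there is some pressure on model size if events are few. If the authors meant collinearity all along, the new sentence only says so.
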